7.8.2.2. Duration of response

For responders (PR or better), duration of response (DOR) is defined as the time from the date of the earliest PR or better to the first documentation of disease progression or death from any cause, whichever occurs first. The censoring convention and analysis method of DOR will be the same as those for PFS in Section 7.8.2.1. DOR will be analyzed for subjects who achieved PR or better (i.e. responders only).

DOR = (first documentation of progression or death – the date of the earliest PR or better + 1) /30.4375 in months.

7.8.2.3. Time to response

For responders (PR or better), time to response (TTR), defined as the time (in month) from the start of study treatment to the date of the earliest PR or better, will be summarized using descriptive statistics for a continuous variable. TTR will not be analyzed using the Kaplan-Meier method for time to event endpoints.

7.8.2.4. Clinical benefit rate

Clinical benefit rate (CBR) is defined as the proportion of subjects who achieve stable disease (SD) or better as the best overall response (BOR) per Lugano criteria (Cheson, 2014) as assessed by the investigator. The summary and analysis method of CBR will be the same as those for ORR as described in Section 7.8.1.

7.8.2.5. Dominant mass response rate

Dominant mass response rate is defined as the proportion of patients who achieve a $\geq 50\%$ decrease from baseline in the sum of products of the greatest perpendicular diameters (SPD) of the target nodal and extra-nodal lesions. The summary and analysis method of dominant mass response rate will be the same as those for ORR as described in Section 7.8.1.

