*Note: CLL patients only: ANC  $\geq 750/\mu\text{L}$  and platelet count  $\geq 30,000/\mu\text{L}$  are acceptable. There are no limits on ANC or platelet count required for patients with leukemic forms of PTCL (ATLL, PLL, LGL) or HSTCL as long as cytopenia, if present, is secondary to disease.*

8. Patient must have adequate renal function as evidenced by a creatinine clearance  $\geq 30$  mL/min (calculated using the Cockcroft-Gault equation or based on a 24-hour urine specimen).
9. Patient must have adequate hepatic function as evidenced by a serum bilirubin level  $\leq 2.0$  mg/dL AND serum AST/ALT levels  $\leq 2.5\times$  the ULN for the reference lab. Serum bilirubin  $\leq 2.5$  mg/dL when increase clearly documented as due to Gilbert's syndrome.
10. Where available, ability to submit a formalin-fixed paraffin embedded tissue (FFPE) block or a minimum of 10 unstained, freshly cut FFPE tissue slides from lymph node or other biopsies that were collected as part of patient diagnosis. If samples are unavailable the patient is still eligible for enrollment.
11. Measureable disease for a given tumor type, defined as:
  - a. The presence of  $\geq 1$  lesion that measures  $\geq 1.5$  cm in a single dimension as assessed by CT, CT/PET for patients with nodal or mass lesions (e.g., FL, DLBCL, other NHL), or
  - b. Quantifiable circulating tumor cells for patients with circulating tumor (e.g., Sézary Syndrome [SS]), or
  - c. For CTCL: mSWAT score  $> 0$ .

12. Ability to provide redacted copies of pathology reports and radiology reports used for the diagnosis of NHL or CLL. In addition, for CTCL, ability to provide redacted photographs of skin responses.

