6. ANALYSIS POPULATIONS

The safety analysis population will consist of all patients treated with at least 1 dose of study medication (cerdulatinib or rituximab). The safety analysis population will be used for all safety analyses. Subjects disposition, demographics, baseline characteristics, and treatment exposure will also be analyzed based on the safety analysis population.

The efficacy analysis population will consist of all patients who have taken at least 1 dose of study medication and have had at least 1 post-baseline investigator response assessment (IRA). The efficacy analysis population will be used for the primary and secondary efficacy endpoints for the follicular lymphoma (FL) patients in Cohort 1 and 2 and the peripheral T-cell lymphoma (PTCL) patients in Cohort 5. In addition, efficacy will also be assessed in the corresponding safety analysis population in Cohort 1, 2, and 5.

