7.1.2. Handling of Missing Data

Missing data will not be imputed unless otherwise specified. Missing dates or partially missing dates will be imputed conservatively for adverse events and prior/concomitant medications/procedures as provided in Appendix A.

When summarizing discrete variables, subjects with missing data are generally included in the denominator to calculate percentage unless otherwise specified. In general, a category of “Missing” will be created and the subjects with missing data will be presented.

When summarizing continuous variables, subjects with missing data are not included in calculations unless otherwise specified.

No imputation of AE grades will be performed. AEs with missing CTCAE grades will only be summarized in the all-grade column. If the assessment of the relationship of an AE to study treatment is missing, the AE is assumed to be related to the study treatment in the summary tables. No imputation will be done in the AE listings.

The reason for lack of sufficient information for response evaluation for FL and PTCL subjects in Cohorts 1, 2, and 5 will be listed with reasons for end of treatment/study, death, and any subsequent anti-cancer therapy if applicable.

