7.8. Efficacy analysis

The efficacy of the Phase 1 patients will be presented in the subject listing only. For Phase 2a patients, efficacy will be summarized and analyzed for the FL patients in Cohort 1 and 2 and the PTCL patients in Cohort 5 only. For FL subjects in Cohort 1 and 2, efficacy will be summarized by number of prior regimens (≤ 3 vs ≥ 4). Efficacy of PTCL will be summarized by pathology subgroup as defined in Appendix B (AITL/TFH vs NOS vs Others). The efficacy listing will be provided for non-FL/non-PTCL patients in Cohort 1, 3, 4, and 6.

All efficacy analyses will be based on the efficacy analysis population. The efficacy analyses will also be analyzed in the corresponding safety analysis population in Phase 2a Cohort 1, 2, and 5 as sensitivity analyses.

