7.8.1. Primary Efficacy Endpoint

Overall response rate (ORR) is defined as the proportion of subjects who achieve partial response (PR) or better as the best overall response (BOR) per Lugano criteria (Cheson, 2014, see appendix C) as assessed by the investigator. BOR is defined as the best response from treatment start to the data cutoff date (inclusive), disease progression (inclusive), or the start of new anti-cancer therapies (inclusive), whichever occurs first.

ORR will be calculated by cohort, and the associated 95% exact confidence interval (CI) will be estimated using the Clopper-Pearson method.

The primary endpoint of ORR may also be analyzed in additional subgroups of the efficacy analysis population as sensitivity analysis.

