If the start day of a subsequent anti-cancer therapy is missing, it will be assumed to be the first day of the month.

5. Cancer Diagnosis

If a cancer diagnosis date is partially missing, impute as follows:

- If both month and day are missing, the imputed value will be Jan 1
- If only day is missing, the imputed day will be the first day of the month
- If end date is completely missing, do not impute

6. Prior Therapy/Response to Prior Therapy

If the day of a prior therapy or response to prior therapy date is missing, set it to 15th of the month. Otherwise, do not impute.

B. Pathology subgroup of Peripheral T-cell Lymphoma (PTCL)

CSR TFL Column	Pathology in EDC
AITL/TFH	AITCL
	PTCL Angioimmunoblastic T-Cell Lymphoma (AITL)
	PTCL with T-follicular helper phenotype
NOS	PTCL (Peripheral T-Cell Lymphoma) -NOS
Others	ATLL
	ATLL
	ATLL, HTLV-1 associated
	CD4+ PTCL, skin only
	CD4+ PTCL, skin-only
	Cutaneous Gamma Delta
	Cutaneous gamma-delta T-cell Lymphoma
	G/D TCL, skin and LN+
	HTLV-1 ATLL
	Hepatosplenic T cell Lymphoma
	Hepatosplenic T-cell Lymphoma
	LGL*
	Monomorphic Epitheliotropic Intestinal T-Cell Lymphoma
	NK/T-cell
	PTCL Anaplastic Large Cell Lymphoma (ALCL) ALK Negative (-)
	Primary Cutaneous Gamma/Delta T-cell Lymphoma
	T-Cell Prolymphocytic Leukemia
	T-cell prolymphocytic leukemia
	aggressive epidermotropic CD8+ **
	gamma-delta T-cell lymphoma
hepatosplenic T Cell lymphoma	
hepatosplenic gamma-delta T cell lymphoma	

*LGL (large granular lymphocytic leukemia) was miscategorized as PTCL at study entry

**CTCL with aggressive epidermotropic CD8+ was miscategorized as PTCL at study entry

C. Lugano Criteria for Response Assessments in NHL (Protocol Amendment 9 Table A4-11).

Response and Site	PET-CT–Based Response	CT-Based Response

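### Dominant mass response keeps patients with no baseline target lesion in its denominator, so any such patients in Cohort 5 pull the reported rate down

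*SAP*

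**What the plan says.** SAP 7.8.2.5 counts a patient as a dominant mass responder after a 50% or greater reduction from baseline "in the sum of products of the greatest perpendicular diameters (SPD) of the target nodal and extra-nodal lesions". The denominator is described only as patients. The section then refers to the ORR method: "The summary and analysis method of dominant mass response rate will be the same as those for ORR as described in Section 7.8.1".

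That method, in SAP 7.8.1, reads: "ORR will be calculated by cohort, and the associated 95% exact confidence interval (CI) will be estimated using the Clopper-Pearson method". The population comes from SAP 7.8: "All efficacy analyses will be based on the efficacy analysis population", with the safety population as a sensitivity analysis. SAP section 6 asks for one dose and one investigator response assessment after baseline. It does not ask for a target lesion. For discrete variables, SAP 7.1.2 adds that "subjects with missing data are generally included in the denominator to calculate percentage unless otherwise specified". Nothing different is specified for this endpoint.

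On eligibility, item 11 of Protocol 4.1.2 gives alternatives joined by *or*: a lesion of at least 1.5 cm, an mSWAT score above zero in CTCL, or "Quantifiable circulating tumor cells for patients with circulating tumor". Protocol 8.1 and Appendix 4 set separate response criteria for the leukemic forms of PTCL, and those for LGL use clinical assessments and blood counts. SAP Appendix B lists ATLL, "T-Cell Prolymphocytic Leukemia" and LGL among the recorded Cohort 5 pathologies and places them all in the Others column.

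**The concern.** A patient with no target lesion has a baseline SPD of zero. The percent change is then undefined and a 50% fall cannot occur, however well the disease responds. An LGL patient could have a complete response on blood counts and still never be a dominant mass responder.

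If such patients stay in the denominator, the rate measures two things at once: how often target masses shrink, and how many patients had target masses to begin with. This works against the endpoint's purpose. SAP section 8 substitutes it for lymph node response so that nodal and extra-nodal target lesions together serve as a measure of tumor burden. SAP 7.8 also summarizes PTCL efficacy by AITL/TFH, NOS and Others. The leukemic types all sit in Others, so that column would carry most of any dilution.

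**Working it through.** **Interval method.** The documents give no figure for dominant mass response itself, but the exact interval it inherits from ORR can be checked against the Protocol Synopsis (Sample Size Considerations). Clopper-Pearson gives:

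- 12/40: 16.6% to 46.5%, as printed.
- 8/40: 9.1% to 35.6%, against a printed upper bound of 35.7%, a rounding difference.
- 1/20: upper bound 24.9%, against the stated approximate 25%.

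**Formula.** Let N be the patients in the analysis set, k those without a baseline target lesion, f = k/N, and x the responders. All x responders come from the N − k patients with target lesions.

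- Rate as the SAP is written: x/N
- Rate among patients with target lesions: p = x/(N − k)
- Hence x/N = p × (N − k)/N = p × (1 − f), and the shift is −p × f.

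**Inputs.** The documents do not give k or f, so a range is assumed. For p, 30% to 40% is used. Protocol 11.1.3 gives that range for response rate in general; applying it to this endpoint is an assumption.

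**Shift in percentage points, p × f:**

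| f | p = 30% | p = 40% |
|---|---|---|
| 0% | 0 | 0 |
| 5% | 1.5 | 2.0 |
| 10% | 3.0 | 4.0 |
| 20% | 6.0 | 8.0 |
| 30% | 9.0 | 12.0 |

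**Same responders, two denominators, N = 40** (within the 40 to 50 evaluable patients planned for an expanded cohort):

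| x | k | x/N (95% CI) | x/(N − k) (95% CI) |
|---|---|---|---|
| 12 | 2 | 30.0% (16.6, 46.5) | 31.6% (17.5, 48.7) |
| 12 | 4 | 30.0% (16.6, 46.5) | 33.3% (18.6, 51.0) |
| 12 | 8 | 30.0% (16.6, 46.5) | 37.5% (21.1, 56.3) |
| 12 | 12 | 30.0% (16.6, 46.5) | 42.9% (24.5, 62.8) |
| 16 | 4 | 40.0% (24.9, 56.7) | 44.4% (27.9, 61.9) |
| 16 | 8 | 40.0% (24.9, 56.7) | 50.0% (31.9, 68.1) |

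**Pathology columns.** If all k patients are in Others and that column holds m patients, their share there is k/m. This is at least k/N, because m cannot exceed N. The documents do not give m, so no figure can be put on it.

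**The case against.** A reader might infer that Cohort 5 did enroll patients with circulating disease only, and that its rate is therefore known to be too low. The documents do not support that. SAP Appendix B is a list of pathology labels, with no counts and no lesion status. Leukemic histology does not imply an absence of target lesions. The ATLL criteria in Protocol Appendix 4 score nodes and extranodal masses by sums of products. PLL is referred to the IWCLL criteria, which use target nodes and SPD. The lesion-selection rules name cutaneous lesions, liver and spleen among possible target sites as well as among non-target examples, so skin-only or hepatosplenic disease need not mean zero SPD. Only LGL is assessed without measuring lesions, and the SAP says it was miscategorized at entry. The one example given for the circulating-disease route is Sézary syndrome, which belongs to Cohort 6, where efficacy is listed only. All of this stands, and it makes the point conditional.

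It can also be said that the SAP never states that these patients are failures. That is true as to wording. SAP 7.1.2 says *generally* and provides for a Missing category, so they may be visible in the table. A Missing row does not take them out of the percentage, however, and sections 6, 7.1.2, 7.8 and 7.8.2.5 read together lead to the full denominator.

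A third argument is that a proportion of all evaluable patients is well defined and conservative, and that the protocol's lymph node response is likewise a proportion of patients with no lesion restriction. This is fair as a matter of estimand. The rate is low only relative to patients in whom the percent change exists. That is a reason to keep the full-denominator version as a sensitivity analysis, since on its own it cannot be read as mass shrinkage.

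Finally, the pathology columns are descriptive summaries and no formal comparison is planned. A claim that a test between subgroups is distorted would go too far. AITL/TFH and NOS should be little affected.

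**Conclusion.** The point holds in conditional form. As written, the SAP puts dominant mass response on a denominator that can include Cohort 5 patients who cannot meet the endpoint, and the effect can only be downward. The factor is (1 − f). For f between 5% and 30% and p between 30% and 40%, the shift is 1.5 to 12 percentage points; at f = 10% it is 3 to 4 points, small beside an exact interval of 16.6% to 46.5% for 12/40. It is zero if every patient has a target lesion. Both ranges are assumptions, because the documents give neither the number of patients without target lesions nor an expected rate for this endpoint.

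Any dilution falls mainly in the Others column. The endpoint is secondary and descriptive, the protocol sets no success criteria, and ORR is untouched. The change is still worth making, because it is cheap and removes a dependence on case mix that a reader of the table could not otherwise see.

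**What to change.** In SAP 7.8.2.5:

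- Set the denominator to patients in the analysis set with at least one baseline target lesion, that is, combined nodal and extra-nodal target SPD above zero.
- Count patients in that set with no post-baseline SPD as non-responders.
- Report the number without target lesions by cohort and, for PTCL, by pathology subgroup.
- Optionally keep the full-denominator rate as a labeled sensitivity analysis.

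The waterfall plot in SAP 7.8.2.6 needs its own set, because it uses target nodal lesions only. It should take patients with baseline target nodal SPD above zero and a post-baseline nodal measurement. A patient whose only target lesions are extra-nodal belongs in the dominant mass denominator but has no defined value for the plot.

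The cost is a sentence or two in each section, a smaller Cohort 5 denominator and a somewhat wider interval. With 12 responders, for example, the width goes from 46.5 − 16.6 = 29.9 points at 12/40 to 51.0 − 18.6 = 32.4 points at 12/36. The sponsor can count the affected patients from its own data, and the rule should be written before the tables are run.

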7.8.2.6. Lymphadenopathy

Tumor burden in lymph nodes as measured by target nodal lesions from CT scans will be plotted in terms of waterfall plot SPD (sum of product of diameters). The best percentage improvement in target nodal lesion SPD will be plotted against subjects. New lesion will not be included in the waterfall plot calculation.

Best % improvement in SPD = (lowest post-baseline SPD of target nodal lesions – baseline SPD of target nodal lesions) / baseline SPD of target nodal lesions X 100%.

7.8.3 Subgroup Analysis

As appropriate (e.g. when there are sufficient number of subjects in the subgroup), the primary efficacy endpoint and selected secondary endpoints will be summarized in the following subgroups for the FL patients in Phase 2a Cohort 1 and 2 and the PTCL patients in Phase 2a Cohort 5:

- Age group (≤ 65 vs > 65)
- Sex
- Prior lines of systemic anti-cancer therapy (≤ 3 vs ≥ 4)
- Baseline ECOG performance score (0 vs ≥ 1)
- Baseline bone marrow involvement (Yes vs No)
- Relapsed vs refractory
- Bulky disease (any target lesion with ≥ 7 cm in LDi or at least 3 target lesions with ≥ 3 cm LDi: Yes vs No)
- Follicular Lymphoma Internal Prognosis Index (FLIPI score, FL patients only)

7.9. Safety Analysis

All safety analyses will be performed in the safety analysis population.

Safety will be primarily assessed on the basis of adverse events (AE) rates. Clinical laboratory data, ECG findings, physical examinations, and vital signs will also be used for determining safety. Descriptive statistics will be used to summarize the safety data. The Phase 1 portion will be summarized by the initial assigned dose level and the Phase 2a portion will be presented by cancer type.

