### Exploratory Efficacy – Phase 2a Only

As an exploratory assessment, patients will be asked to complete a Global Health Assessment (Appendix 8) to assess whether patients feel their overall health is improving on this study. The correlation between markers of inflammation with clinical response and the overall health (Global Health Assessment) will be assessed.

An additional exploratory assessment, detection of minimal residual disease (MRD) in CLL patients achieving a CR or CRi or PR will also be performed using at least 4 color flow cytometry by either local lab or a designated central lab in blood and/or marrow. MRD- (MRD negativity) defined as < 1 CLL cell in 10,000 leucocytes. MRD+ (MRD positivity) is defined as ≥ 1 CLL cell in 10,000 leucocytes.

*Pharmacokinetic Analyses:* PK parameters will be calculated for each patient for which adequate samples are available and summarized.

*Pharmacodynamic Analyses, Phase 1 and 2a:* A number of PD parameters (described above) will be measured serially. At each time point, each of these parameters will be summarized by dose level. In addition, the parameters over time will be plotted for each patient and dose cohort. No formal statistical analyses are planned.

*Safety, Phase 1 and 2a:* For the Phase 1 portion of the study, the primary safety endpoint is the incidence of DLT by dose level and the secondary safety endpoints are the AE profile (classified by NCI-CTCAE v5.0), clinically significant changes in vital signs and physical exams by dose level, and changes in hematology and chemistry laboratory parameters by dose level. The incidence of DLT will be summarized and listed by dose cohort for Phase 1.

For the Phase 1 and Phase 2a portions of the study, AEs will be graded according to the National Cancer Institute Common Toxicity Criteria for Adverse Events (NCI-CTCAE) v5.0 and coded according to the latest Medical Dictionary for Regulatory Activities (MedDRA) version available at the time of database creation. The number and percent of patients with any AE will be presented by System Organ Class (SOC) and preferred term for each cohort will be summarized by dose cohort for Phase 1 and by Cohort for Phase 2a. An additional summary will include all patients who received the dose used in Phase 2a. Vital signs, laboratory parameters, and ECG intervals will be summarized and listed by time point for each dose cohort for Phase 1 and by cohort for Phase 2a. No formal statistical analyses are planned.

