##### 2.1.2.2. *Secondary Objectives*

- To assess the duration of antitumor activity of cerdulatinib, amount of time to achieve tumor response, and magnitude of response.
- To further evaluate the PK profile of cerdulatinib in patients with specific subtypes of B-cell or T-cell NHL, alone or in combination with rituximab for B-cell NHL.
- To further evaluate the PD of cerdulatinib in patients with specific subtypes of B-cell or T-cell NHL, alone or in combination with rituximab for B-cell NHL.
- To assess tumor phenotype and genotype in relation to clinical response.
- To further evaluate the safety and tolerability of cerdulatinib in patients with specific subtypes of B-cell or T-cell NHL, or CLL/SLL.

- To evaluate the safety and tolerability of the combination of cerdulatinib with rituximab for B-cell NHL.

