#### **4.1.3. Phase 2a Cohort-specific Inclusion Criteria**

##### **4.1.3.1. Cohort 1 (FL) – Grades 1 to 3A (Single-agent Cerdulatinib)**

1. Received  $\geq 1$  prior treatment regimen.

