#### **11.1.6. Safety Analyses, Phase 1 and 2a**

The primary safety endpoint is the incidence of Grade 3 or higher clinically significant toxicity by dose level, and the secondary safety endpoints are as follows:

- Adverse event profile (classified by NCI-CTCAE v5.0).
- Clinically significant changes in vital signs, physical exams by dose level.
- Changes in hematology and chemistry laboratory parameters by dose level.

The incidence of Grade 3 or higher clinically significant toxicity will be summarized and listed by dose cohort for Phase 1.

Adverse events (AEs) will be graded according to the NCI-CTCAE v4.0 (Phase 1) and NCI\_CTCAE v5.0 (Phase 2a) and coded according to the latest MedDRA version available at the time of database creation. The number and percent of patients with any AE will be presented by System Organ Class (SOC) and preferred term for each cohort will be summarized by dose

cohort for Phase 1 and by Cohort for Phase 2a. An additional summary will include all patients who received the dose used in Phase 2a.

Vital signs, laboratory parameters, and ECG intervals will be summarized and listed by time point for each dose cohort for Phase 1 and by Cohort for Phase 2a. No formal statistical analyses are planned.

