3.2.2. Secondary Objectives

- To assess the duration of antitumor activity of cerdulatinib, amount of time to achieve tumor response, and magnitude of response.
- To further evaluate the PK profile of cerdulatinib in patients with specific subtypes of B-cell or T-cell NHL, alone or in combination with rituximab for B-cell NHL.
- To further evaluate the PD of cerdulatinib in patients with specific subtypes of B-cell or T-cell NHL, alone or in combination with rituximab for B-cell NHL.
- To assess tumor phenotype and genotype in relation to clinical response.
- To further evaluate the safety and tolerability of cerdulatinib in patients with specific subtypes of B-cell or T-cell NHL, or CLL/SLL.

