7. STATISTICAL METHODS

7.1 Data Analysis General Considerations

Where applicable, descriptive statistics will be provided. For continuous variables, n, mean, standard deviation (SD), median, minimum, and maximum will be presented. For discrete variables, the frequency and percentage will be presented. For time to event variables, unless specified otherwise, the Kaplan-Meier (KM) estimate and corresponding two-sided 95% confidence intervals (CIs) will be presented for the median and quartiles and, as necessary, for the event-free rates at the selected time points.

All calculations and analyses will be performed using SAS version 9.4 or higher.

Unless specified otherwise, the Phase 1 portion will be summarized by the initial assigned dose level and the Phase 2a portion will be presented by cancer type. Summaries and analyses will be done for Phase 1 and Phase 2a separately. There will be no pooling of Phase 1 and Phase 2a data. For the subjects enrolled in Phase 1 but continued in Phase 2a, only baseline information (baseline demography, disease characteristics, and prior anti-cancer therapies) from Phase 1 database will be used for corresponding Phase 2a summary tables, all other data will remain separate in Phase 1 and Phase 2a summary tables unless specified otherwise.

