- Rituximab-related TEAEs by SOC, PT (Cohort 2 only)
- Rituximab-related TEAEs by SOC, PT, and maximum severity grade (Cohort 2 only)
- Serious TEAEs by PT
- Serious TEAEs by SOC, PT
- TEAEs leading to cerdulatinib discontinuation by PT
- TEAEs leading to cerdulatinib discontinuation by SOC, PT
- TEAEs leading to cerdulatinib reduction by PT
- TEAEs leading to cerdulatinib reduction by SOC, PT
- Fatal TEAEs by PT
- Fatal TEAEs by SOC, PT.

TEAEs leading to rituximab dose modifications and discontinuations will be listed only.

Summaries (all-grade and grade 3 or above) will be provided for cytopenia category by combining following preferred terms in the AE dataset:

- Neutropenia: neutropenia, neutrophil count decreased, febrile neutropenia
- Thrombocytopenia: thrombocytopenia, platelet count decreased
- Anaemia: anaemia.
- Leukopenia: leukopenia, white blood cell count decreased
- Lymphopenia: lymphopenia, lymphocyte count decreased

For the following categories of TEAEs of special interest, the time to the first onset of the event will be analyzed (e.g. median/mean and min/max).

- All-grade gastrointestinal disorders of special interest
- Grade 3 or higher gastrointestinal disorders of special interest
- All-grade infections of special interest (lower respiratory bacterial infections)
- Grade 3 or higher infections of special interest (lower respiratory bacterial infections)

The relationship between all-grade infections of interest and concomitant compliance use of antimicrobial prophylaxis will be explored. In addition, gastrointestinal disorders and infections of special interest may be analyzed for certain population subgroups as appropriate.

In addition, selected safety summaries will be repeated for the subset of phase 2a subjects with 30 mg BID as starting cerdulatinib dose.

A summary of the number of deaths and the primary cause of death, classified by deaths within 30 days of last dose of study drug and deaths beyond 30 days after the last dose, will be provided.

7.8.1.1. Dose limiting toxicity in Phase 1

The number and percentage of patients experiencing dose limiting toxicities as captured in the eCRF by the investigator during Phase 1 will be summarized by initial dose cohort.

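### The SAP's by-cancer-type rule for Phase 2a safety does not keep single-agent FL (Cohort 1) apart from FL on cerdulatinib plus rituximab (Cohort 2) in the main adverse event tables, and the combination-safety objective is dropped without record

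*SAP*

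**What the plan says.** The protocol sets the display unit for Phase 2a safety twice. The synopsis, in the safety paragraph of its statistical methods, has adverse events "summarized by dose cohort for Phase 1 and by Cohort for Phase 2a". Protocol 11.1.6 repeats this for adverse events and applies the same rule ("cohort for Phase 1 and by Cohort for Phase 2a") to vital signs, laboratory parameters and ECG intervals.

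The SAP uses a different unit. Section 7.1 gives a default that opens "Unless specified otherwise, the Phase 1 portion will be summarized by the initial assigned dose level" and puts Phase 2a by cancer type. Section 7.9 repeats it for safety: "the Phase 2a portion will be presented by cancer type". Cancer type is not defined.

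Protocol 2.1.2.2 lists six Phase 2a secondary objectives, the last being "To evaluate the safety and tolerability of the combination of cerdulatinib with rituximab for B-cell NHL". SAP 3.2.2 carries five and ends at "To further evaluate the safety and tolerability of cerdulatinib in patients with specific subtypes of B-cell or T-cell NHL, or CLL/SLL". SAP Section 8, which lists changes from the protocol, mentions the narrowed efficacy scope, the switch to dominant mass response and the mixed CTCAE versions. It mentions neither the new display unit nor the missing objective.

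**The concern.** Cohort 1 is headed "Cohort 1 (FL) – Grades 1 to 3A (Single-agent Cerdulatinib"), and Cohort 2 is FL of the same grades on cerdulatinib plus rituximab. The prior-treatment criterion is the same for both. Cancer type cannot tell them apart; only treatment can.

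The protocol treats the safety of the combination as a question in its own right. It is a named objective, and under Protocol 7.6 the Study Committee reviews the first 3 to 6 combination patients after Cycle 1 before further enrolment. Protocol 1.6.2 names infusion reactions, tumor lysis syndrome, hematotoxicity and infections as rituximab effects. Cytopenias and infections are also categories that the SAP singles out for summary. If the two cohorts share a column, a reader can take neither the single-agent FL profile nor the combination profile from the main tables.

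**Working it through.** No figure in the plan is at issue, so the check is mainly of text.

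**1. Is cancer type just another word for cohort?** The SAP's own usage suggests not. It writes by cohort for ORR (7.8.1, Primary Efficacy Endpoint), vital signs, QTcF, ECOG status and the Global Health Assessment, and it plans separate PFS curves for Cohorts 1 and 2 (7.8.2.1). Section 7.8 refers to non-FL patients inside Cohort 1, so one cohort can hold more than one cancer type. Conversely, one cancer type, FL Grade 1 to 3A, spans two cohorts.

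**2. Which Phase 2a safety displays separate Cohort 2?**

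| Display in the SAP | Unit stated | Separates Cohorts 1 and 2? |
|---|---|---|
| Rituximab-related TEAEs (three tables) | Cohort 2 only | Yes, but a causality subset |
| Vital signs; QTcF | Cohort | Yes |
| TEAEs leading to rituximab modification or discontinuation | Listing | Listing only |
| All, Grade 3 or higher, cerdulatinib-related, serious and fatal TEAEs; TEAEs leading to cerdulatinib reduction or discontinuation | None, so the 7.9 rule applies | No |
| Laboratory values; exposure | None, so the default applies | No |

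The SAP's one further planned split, "selected safety summaries will be repeated for the subset of phase 2a subjects with 30 mg BID as starting cerdulatinib dose", is by starting dose and does not separate the treatments.

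**3. Do the Cohort 2 tables fill the gap?** They include an event only if the investigator relates it to rituximab, or if the relationship is missing and the SAP assumes it. Events in Cohort 2 attributed to cerdulatinib alone, or judged unlikely or unrelated for rituximab, are left out. Overall tolerability of a combination needs all events, whatever the attribution.

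**4. How large could the distortion be?** If the columns are pooled, the displayed rate is (n1 × p1 + n2 × p2) / (n1 + n2), with 1 for single agent and 2 for combination. Planned cohort sizes are about 20 to 50 (Protocol 11.2.2, SAP 5.2). The rates below are assumptions, because the documents give none by cohort.

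| n1, n2 | p1, p2 | Pooled | Minus p1 | Minus p2 |
|---|---|---|---|---|
| 40, 40 | 30%, 50% | (12 + 20)/80 = 40.0% | +10.0 | -10.0 |
| 50, 20 | 30%, 50% | (15 + 10)/70 = 35.7% | +5.7 | -14.3 |
| 20, 50 | 30%, 50% | (6 + 25)/70 = 44.3% | +14.3 | -5.7 |
| 50, 20 | 30%, 40% | (15 + 8)/70 = 32.9% | +2.9 | -7.1 |
| 20, 50 | 30%, 40% | (6 + 20)/70 = 37.1% | +7.1 | -2.9 |
| any | 30%, 30% | 30.0% | 0 | 0 |

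Differences are in percentage points.

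**The case against.** The best defence is that the SAP never says the two cohorts share a column. Protocol 3.1 describes the cohorts as defined by cancer type and prior therapy, SAP Section 2 calls them disease cohorts, and most Phase 2a displays with a stated unit are by cohort. A programmer might well produce separate FL columns. This stands in part: pooling is the natural literal reading, not an explicit instruction. It does not rescue the rule, because the SAP uses the two terms differently and an analysis plan should not leave the columns of its main safety tables to inference.

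A reader might go further and infer that the combination objective cannot be answered. The documents do not support that. Three Cohort 2 tables of rituximab-related events, by-cohort vital signs and QTcF, and listings of all reported TEAEs are planned. The SAP also states that it is based on Amendment 9, so leaving out a bullet does not cancel the protocol objective. What is missing is an overall Cohort 2 table of all, Grade 3 or higher, serious or fatal events.

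A reader might also infer that the single-agent FL results are contaminated. That needs both pooled columns and different true rates, and the documents establish neither.

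Finally, Phase 2a is exploratory, its safety analysis is descriptive, and cohort is a known variable, so tables can be re-cut later. That limits the harm, and equally makes the correction easy.

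**Conclusion.** The point holds in this form: the SAP replaces the protocol's by-Cohort rule with one that, followed literally, merges single-agent and combination FL patients in the main adverse event tables. It leaves the combination-safety objective without any specified overall adverse event table, drops that objective from its own list, and declares neither change.

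The textual findings rest on no assumption. The size does. Under the assumed rates above, the single-agent error runs from +2.9 to +14.3 points; with equal rates it is zero, although a pooled column could not show that the rates were equal. These figures illustrate the mechanism and do not estimate this trial's error. How safety is displayed across starting doses is a separate question and forms no part of this conclusion.

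**What to change.** - In SAP 7.1 and 7.9, state that all Phase 2a safety and exposure tables show Cohort 1 FL and Cohort 2 FL plus rituximab in separate columns. Give the non-FL patients in Cohort 1 their own stated column, so that nobody is left without one.
- Restore the combination-safety objective in SAP 3.2.2.
- Record any remaining departure from the protocol's by-Cohort rule in SAP Section 8.

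No new data are needed. The cost is one or two more columns per safety table and smaller denominators: in a column of 20, one patient is 1/20 = 5 percentage points, so small differences between the FL columns should not be over-read. The change is best made before the tables are produced.
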